8.3.3 Safety Population

Safety Analysis Set (SAS): The SAS- Set will comprise all subjects who received at least one administration of study medication at any dosage and for any period of time.

8.4 Methods of Statistical Analysis

8.4.1 General Statistical Considerations

All statistical analyses will be performed and all summary tables and data listings will be prepared using the most recently installed version of the Statistical Analysis System® (SAS) software at the time of statistical analysis. For continuous variables, summary statistics (mean, standard deviation, median, minimum and maximum values) will be tabulated. For discrete variables, the frequency distribution will be tabulated. Statistical tests will be of descriptive nature only except for the analysis of the responder rate.

The following chapter describes the planned statistical analyses at the time of writing the study protocol. More details about the statistical analyses will be provided in the separate Statistical Analysis Plan (SAP), which will be finalized before enrolment of the first subject. Any changes in the statistical methods compared to the final SAP will be documented in the integrated Clinical Study Report.

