I agree to comply with the International Conference on Harmonization Tripartite Guideline on Good Clinical Practice, all applicable national regulations as well as the requirements of the appropriate Institutional Review Board/Independent Ethics Committee and any other institutional requirements.

I agree to ensure that the confidential information contained in this document will not be used for any purpose other than the evaluation or conduct of the clinical investigation without the prior written consent of the study sponsor.

Signature

Date (DD Month YYYY)

Investigator

Investigator's Institution

SYNOPSIS

Protocol code.	SAIL
Protocol version (Date)	Version 3.1, dated 13.01.2017
Detailed title	Evaluation of Ara-C and Idarubicin in Combination with the Selective Inhibitor of Nuclear Export (SINE) Selinexor (KPT-330) in Patients with relapsed or refractory AML
EudraCT no.	2014-000526-37
LKP according to §4 Abs. 25 and §40 Abs. 1 Nr. 5 AMG	[name]. [name], Hannover
Sponsor	GSO Global Clinical Research B.V. EBC Amsterdam [name] The Netherlands
Study design	
Multi center, open-label, non-randomized Phase 2 trial.
 
Patients with relapsed/refractory Acute Myeloid Leukemia (AML) will receive standard chemotherapy cytosine arabinose (Ara-C) 100mg/m² days 1-7 and Idarubicin 10 mg/m² days 1, 3, 5 every 4 weeks (max. 2 cycles) and Selinexor as a flat dose of 60 mg twice weekly during weeks 1-3 of a 4-week cycle starting on Day 2 of week 1 (total of 6 doses per induction cycle).
 
If a bone marrow CR or CRI was achieved the patient will be recommended for stem cell transplantation, which represents the end of study treatment.
 
If a partial remission was achieved an additional induction cycle will be initiated.
 
Patients achieving CR or CRI, who are not eligible for SCT will receive consolidation therapy with AraC (3 cycles) in parallel to maintenance with Selinexor until relapse.
 
Patients with >50% blast reduction after 2 cycles will continue maintenance with Selinexor until PD.
 
Patients will be evaluated for disease status at the end of each 4-weeks induction cycle and approximately every 3 months after allogeneic SCT or CR (or CRI) has been achieved until relapse or death, whichever is first.

Duration of study	
The planned number of 40 patients was reached.
 
End of enrolment period: June 2016.
 
End of study is defined as 2 years after registration of last patient

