3.2 Study timelines

The planned number of 40 patients was reached. The end of the enrolment period was June 2016. End of study will be defined 2 years after registration of the last patient.

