Secondary objectives of the study are 1) To determine the efficacy of Selinexor in combination with standard chemotherapy in patients with relapsed/ refractory AML by:

- Rate of partial remissions
- Percentage of patients being transplanted after induction therapy
- Early death rate
- Overall survival (OS)
- Event-free survival (Events are defined as Death, not achieving a CR or CRi, Relapse after CR or CRi) and

2) To evaluate overall safety and tolerability of Selinexor.

3 Design and type of the study

This is a phase II non-randomized, single-arm, open-label, multicentre study in patients with relapsed or refractory AML.

4 Study variables

The following variables will be evaluated.

The demographic and baseline variables:

Gender, age, race, details on leukemia diagnosis, prior therapy, medical history, current symptoms and residual toxicities from prior therapies, ECOG performance status, clinical neurological examination, cardiac evaluation, disease status, concomitant medication, prior transplantation, primary or secondary AML, early/late relapse from first therapy, mutation, karyotype risk category.

The primary efficacy variable:

The rate of complete responders according to the Cheson criteria.

The secondary efficacy variables:

Rate of partial remissions, percentage of patients being transplanted after induction therapy, early death rate, Overall survival (OS), Event-free survival (EFS), Recurrence-free-survival (RFS)

The safety variable:

Adverse events (AE), blood pressure, pulse, temperature, physical examination, urine analysis, hematology, clinical chemistry, coagulation tests.

5 Sample size considerations

The sample size calculation is based on the evaluation of response rates according to Fleming using the A'Hern extension (Sample size tables for exact single-stage phase II designs. Statist. Med. 2001;20:859-866). In Fleming's procedure to response levels p_0 and p_1 are specified, where p_0 is the largest proportion of responders, which would clearly imply that the treatment does not warrant further investigations and p_1 the minimum required proportion of responders that would imply that the treatment warrant further investigations. The following characteristics were specified in the sample size calculation:

- $p_0 = 0.30$
- $p_1 = 0.60$
- $\alpha = 0.05$ (one-tailed) and
- $\beta = 0.10$

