13.3 Other safety variables

Vital signs (blood pressure, heart rate, temperature) will be summarized with descriptive statistics by visit and dosing group. In addition, the changes from baseline values will be given. The changes from baseline will be analyzed by ANOVA method if feasible. Physical examination, ECG and ECOG results will be summarized with frequency tables.

14 Completion and premature discontinuation

Completion and premature discontinuation will be listed. The reasons for premature discontinuation will be presented.

15 Deviations from the analyses planned in the study protocol

The primary hypothesis of the study was clarified in the Statistical Analysis Plan compared to the definition in the protocol.

16 Execution of statistical analyses

Statistical analyses will be performed by 4Pharma Ltd.

17 Hardware and software

Statistical analysis, tables and patient data listings will be performed with SAS[®] version 9.3 for Windows (SAS Institute Inc., Cary, NC, USA).

18 References

Clinical Study Protocol, Final Protocol, Version 2 (25.08.2015)

19 Appendices

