14.3.4 Other safety variables

- Table 14.3.4.1 Descriptive statistics of vital signs by visit
- Table 14.3.4.2 Change from baseline in vital signs
- Table 14.3.4.3 Descriptive statistics of body weight by visit
- Table 14.3.4.4 Change from baseline in body weight
- Table 14.3.4.5 Review of physical examination
- Table 14.3.4.6 Frequency tables for ECG by visit
- Table 14.3.4.7 Frequency tables for ECOG by visit

EudraCT No.: 2014-000526-37

Study Code: SAIL

Study Title: An Investigator-Initiated Study To Evaluate Ara-C and Idarubicin in Combination with the Selective Inhibitor Of Nuclear Export (SINE) Selinexor (KPT-330) in Patients with Relapsed Or Refractory AML

Addendum to Statistical Analysis Plan dated 2017Aug25

Addendum to Statistical Analysis Plan dated 2017Aug25

Date and version of the addendum: Version 1, 2018Apr04

Sponsor: GSO Global Clinical Research B.V.

Principal Investigator: [name]. [name], Hamburg

The addendum to the Statistical Analysis Plan was approved by:

10 Apr 2018

[figure not shown]
Date

Signature [name], [name]
CEO GSO Global Clinical Research B.V.
Medical Writer

SA
10 Apr 2018

94.18

Date

Signature [name]. [name],
University Hospital Hamburg-Eppendorf

1. Purpose of the addendum to SAP

The purpose of this addendum to the Statistical Analysis Plan (SAP) dated 2017Aug25 is to clarify the analysis of the primary endpoint and to add an analysis of the difference between the subgroups.

2. Analysis of the primary endpoint

The primary objective of the clinical trial is to determine the efficacy of Selinexor in combination with standard chemotherapy in patients with relapsed/refractory acute myeloid leukemia (AML) by determination of rate of complete remission (CR) or morphologic complete remission with incomplete blood count recovery (CRi), as defined by the recommendations on diagnosis and management of AML in adults from an international expert panel, on behalf of the European LeukemiaNet.

The primary endpoint is defined as the percentage of patients achieving a CR or CRi. Patients with morphologic leukemia free-state (MLFS) shall be included into the group of responders.

To determine the efficacy of Selinexor in combination with standard chemotherapy, the best response after Selinexor treatment shall be analysed, thus the best response after the induction cycle(s).

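### The protocol promises a SAP final before the first patient enrols, but the only SAP identified is dated about 14 months after enrolment closed in an open-label trial, and SAP 15 declares only one of its departures from the protocol

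*Protocol*

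**What the plan says.** Protocol 8.4.1 leaves the statistical detail to a separate SAP, "which will be finalized before enrolment of the first subject". The study report is then to document changes measured against that final SAP.

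The protocol carrying this sentence is "Version 3.1, dated 13.01.2017". Its section 3.2 says "The planned number of 40 patients was reached" and "The end of the enrolment period was June 2016".

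The SAP's date comes from the header of its addendum: "Addendum to Statistical Analysis Plan dated 2017Aug25". SAP 18 cites Protocol Version 2 of 25 August 2015, not Version 3.1. SAP 3 describes the trial in these words: "This is a phase II non-randomized, single-arm, open-label, multicentre study in patients with relapsed or refractory AML".

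Under deviations from the protocol, SAP 15 has one entry: "The primary hypothesis of the study was clarified in the Statistical Analysis Plan compared to the definition in the protocol".

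The addendum is Version 1 of 4 April 2018. Its section 3 refers to an initial analysis already done.

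**The concern.** A reader of Protocol 8.4.1 would take every analysis in the SAP as fixed before any patient was treated. The dates rule that out for the only SAP identified. In an open-label single-arm trial of 40 patients, responses are visible as they occur. Analyses first written down after enrolment therefore lack the protection that the sentence claims.

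The reporting rule makes this worse. Because the study report need only list changes against the final SAP, anything that first appears in the SAP would pass as prespecified unless SAP 15 declares it. At stake is how much weight to give recurrence-free survival (RFS), the transplant-censored curves, the subgroups, event-free survival (EFS) as analysed, and a response rate that includes MLFS.

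**Working it through.** **Inputs.** End of enrolment, June 2016 (Protocol 3.2). Protocol version, 13 January 2017 (synopsis). SAP, 25 August 2017 (addendum header). Addendum, 4 April 2018. Treatment start within two weeks of enrolment (Protocol 3.1). At most two 4-week induction cycles (Protocol 3.1.2). Months are days / 30.4375.

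**1. The protocol's own rule reproduces.** With N = 25, p0 = 0.30 and z = 1.645 (Protocol 8.2):
- 25 × 0.30 + 1.645 × √(25 × 0.30 × 0.70) = 7.5 + 1.645 × 2.291 = 11.27. The nearest integer is 11, plus 1 gives 12.
- Exact binomial: P(X ≥ 12) is 0.0442 at 0.30 and 0.922 at 0.60.
- Additional cohort, 8 of 14: 0.031 at 0.30, 0.816 at 0.65 and 0.907 at 0.70.

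The cut-off uses only N, p0 and alpha. Protocol 8.1 and SAP 6 both set the null at 30% or less. Restating the alternative from at least 60% to over 30% therefore leaves the 12-of-25 rule where it was.

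**2. Gap between enrolment and SAP.**
- From 30 June 2016: 421 days / 30.4375 = 13.8 months.
- From 1 June 2016: 450 days / 30.4375 = 14.8 months.

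The first-enrolment date is not needed: a SAP dated after the last enrolment cannot precede the first. Protocol 3.1 was itself dated 421 − 224 = 197 days (6.5 months) after 30 June 2016.

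**3. Could responses be seen?** Assume registration by 30 June 2016, start 14 days later and two full cycles: 14 + 56 = 70 days, so the last induction response was due by about 8 September 2016. That is 351 days, or 11.5 months, before the SAP date.

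**4. SAP against the supplied protocol.**

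| Item | Protocol 8.4.3 | SAP | New analyses |
|---|---|---|---|
| RFS | not listed | secondary variable (4, 12.2) | 1 |
| OS, RFS, EFS censored at transplant | not listed | additional analyses (12.3) | 3 |
| Response by AML type, remission length, prior transplant, karyotype, mutation | not listed | subgroups (12.1) | 5 |
| EFS | death, no CR/CRi, or relapse | runs from CR/CRi to death or relapse (12.2) | redefined |

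1 + 3 + 5 = 9 distinct additions, plus one redefinition. A clock that starts at CR/CRi cannot count failure to reach CR/CRi. SAP 2 still repeats the protocol's three-event definition, so the SAP also disagrees with itself. The split by dosing schedule is left out of the nine because Protocol 8.2 already treats the 15 additional patients separately.

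**5. Disclosure.** SAP 15 declares the hypothesis wording only. It does not mention the nine additions, the EFS change or the SAP's own date.

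**6. Addendum.** It is dated 222 days (7.3 months) after the SAP. It counts MLFS as response, limits best response to the induction cycles (the initial analysis had used the whole study period) and adds p-values for differences between subgroups.

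**The case against.** The strongest reply is that a SAP finalised before database lock is acceptable in an open-label trial. SAP 7 places the data review before lock, in the future tense, so the SAP reads as a pre-lock document. Timing is compatible with this. For a patient registered on 30 June 2016 who started 14 days later and took the maximum year of treatment, the trigger in Protocol 5.2.7 (30 days after last dose) would fall about 13 August 2017, twelve days before the SAP. This stands. A reader might infer that the SAP's choices were made to suit the results. The documents show only that responses could have been seen, not that anyone used them. One post hoc label for both SAP and addendum would also be wrong, since only the addendum is known to follow an analysis.

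The SAP was written against Protocol Version 2, which is not supplied, and an earlier SAP version is not excluded. This stands too. The nine additions are relative to Version 3.1. Equally, presence in the supplied Protocol 8 does not prove prespecification, because that version also postdates enrolment and contains the rule for the 15 additional patients.

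A reader counting tables and figures in SAP 19.2 might conclude that 14 of 30 efficacy outputs are new. That counts RFS three times and the three transplant-censored repeats six times. Four of those six are alternative-censoring versions of OS and EFS, which the protocol does list. Nine analyses is the fair count.

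The change of alternative hypothesis might look like a lowered bar. It is not: the null and the cut-off are unchanged, and SAP 15 discloses it.

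Finally, Protocol 8.4.1 makes all tests descriptive except that of the responder rate, and SAP 12.2 and 12.3 plan Kaplan-Meier summaries without tests. That limits the harm, but it does not correct the statement about timing or the undeclared EFS change.

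**Conclusion.** The point holds as a matter of stated against actual prespecification. Version 3.1 promises a SAP before the first patient at a time when enrolment was already complete, and the only SAP identified follows the end of enrolment by 13.8 to 14.8 months. Relative to the supplied protocol, nine analyses and one endpoint redefinition enter through the SAP undeclared. Three further changes enter through the addendum after an initial analysis, and the inclusion of MLFS affects the primary endpoint directly.

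The CR/CRi endpoint, p0 = 30% and the 12-of-25 rule stand in the protocol and do not depend on the SAP date.

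This rests on 25 August 2017 being the date of the first final SAP and on Version 3.1 as the comparator. The documents do not support a finding that results were consulted when the SAP was written.

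**What to change.** Do not silently delete the sentence in Protocol 8.4.1. State in SAP 15 and in the study report that the commitment was not met, and give the dates of the SAP, the addendum, database lock and the first analysis.

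Add one table that lists each efficacy analysis with the document version and date that introduced it:
- **(a) In the protocol**, with the version date, including the later rule for the 15 additional patients and EFS as defined in 8.4.3.
- **(b) First defined or changed in the SAP after enrolment closed**: RFS, the transplant-censored repeats, the five subgroup factors and the EFS redefinition. Report these as exploratory and not prespecified before enrolment.
- **(c) Added or changed in the addendum after the initial analysis**: MLFS as response, best response limited to induction, and the subgroup p-values. Report these as post hoc.

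Rest the primary efficacy conclusion on CR/CRi under the Protocol 8.2 rule, and show the result that counts MLFS separately.

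The cost is one declaration and one table, with no change to data or conduct. The downside is a more modest claim for RFS, the subgroups and the MLFS-inclusive rate.

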8.4.2 Demographics and Baseline Characteristics

The following baseline conditions will be analyzed and described:

- Age, gender, ethnic background
- Details on leukemia diagnosis including WHO subtype, cytogenetics and molecular investigations such as FLT3 and NPM-1 mutations
- Details on prior therapy, including start and stop dates, disease progression during or after therapy, as well as discontinuation due to toxicities
- Previous and concurrent relevant diseases
- Current symptoms and/ or residual toxicities from prior therapies
- Body height and weight, BSA
- ECOG performance status
- Standard clinical neurological examination
- Cardiac evaluation
- Calculation (or measurement) of GFR
- HIV testing
- Assessment of disease status
- Concomitant medication

8.4.3 Efficacy Evaluation

Primary Efficacy Parameter

The primary efficacy measure will be the rate of complete responders (CR). Disease status will be assessed by bone marrow and peripheral blood analysis at the end of each 4-weeks induction and consolidation cycle. Disease status during maintenance will be evaluated by peripheral blood analysis at the end of each cycle and during follow-up after SCT every 3 months \pm 28 days. Bone marrow aspirate during maintenance and FU is required in case peripheral blood analysis is suspicious for progression of disease/relapse. Response is evaluated according to Döhner et al. criteria¹.

Secondary Efficacy Parameters

The secondary efficacy measures will be:

- Rate of partial remissions
- Percentage of patients being transplanted after induction therapy
- Early death rate
- Overall survival (OS)
- Event-free survival (Events are defined as Death, not achieving a CR or CRI, Relapse after CR or CRI)

8.4.4 Safety Evaluation

Safety evaluation will comprise the following variable and their change from baseline:

- Blood pressure, pulse, temperature
- Physical examination
- Urine analysis
- Hematology
- Clinical chemistry
- Time of recovery of platelets and ANC
- Coagulation tests

The number of patients developing adverse experiences will be tabulated [NCI CTCAE] Version 4.03. The CTC v4.03 will be the basis for grading the laboratory changes. Additionally, the subset of adverse experiences considered treatment-related will be summarized. Listings of adverse experiences leading to treatment discontinuation and those identified as 'severe' or of 'maximal' severity will be provided.

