10 DATA MONITORING COMMITTEE

An independent Data Monitoring Committee (DMC) will be implemented that reviews accumulating data of the clinical trial with respect to any potential safety issues, study progress and critical efficacy endpoints. The DMC will function in accordance with the principles of the following documents: EMA guideline on data monitoring committees (EMEA/CHMP/EWP/5872/03 Corr), ICH Note for guidance E3 (structure and content of clinical study reports), ICH Note for guidance E6 (Good Clinical Practice), ICH Note for Guidance E9 (Statistical Principles for Clinical Trials) and Directive 2001/20/EC relating to the implementation of good clinical practice in the conduct of clinical trials on medical products for human use.

The DMC will be an independent board consisting of 2-3 physicians with special expertise in AML. A physician is not allowed to participate in this clinical trial while serving on the DMC. The DMC will be supported by an independent statistician, if necessary.

The DMC will review safety data, recovery times and efficacy of the clinical trial and support the interpretation of clinical trial results.

A DMC charter will be set up which defines the roles and responsibilities of the DMC.

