7.3 Safety set

The Safety set will comprise all subjects who received at least one administration of the study medication at any dosage and who have a subsequent safety measurement available.

8 General statistical considerations

The aim of the study is to evaluate the effect of Selinexor in patients with relapsed / refractory AML by complete response rate (CR or CRi).

All background, primary and secondary efficacy variables, and safety variables will be summarized by visit and treatment group. In addition to absolute values, changes from baseline values will be summarized, if feasible.

Summary statistics will include at least the number of patients, mean, standard deviation, median, minimum and maximum for continuous variables, and frequencies and percentages for categorical variables. The results of statistical tests (including 95% CIs) will be included in the tables, when appropriate.

If the assumptions of the parametric statistical test are not met, the use of common transformations (e.g. logarithmic, square root) will be considered. Appropriate non-parametric methods will be used if normality assumptions are not met even after transformations.

In the statistical analyses a p-value less than 0.05 will be considered as statistically significant. If not stated otherwise, all tests will be performed as two-sided and two-sided 95% CIs will be produced for the treatment differences. No adjustments for the p-values will be made. Missing values will not be imputed in the analyses.

Subgroup analyses by dosing schedule (Selinexor / mm² vs. flat dose of Selinexor) will be conducted for all study data.

The table and figure plan is presented in Appendix 18.2.

9 Demographic and other baseline characteristics

All background and other baseline characteristics will be tabulated with descriptive statistics. Medical history and other medication will be summarized with frequency distributions. Tabulations will be conducted overall and by dosing schedule. No statistical tests will be carried out for any baseline measures between the dosing schedules.

10 Concomitant medication/treatment

Concomitant medication and treatments will be summarized overall and by dosing group using ATC classification.

11 Extent of exposure and compliance

The extent of exposure and treatment compliance will be summarized descriptively overall and by dosing schedule.

12 Analysis of efficacy

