12.2 Secondary efficacy variables

The secondary efficacy variables; rate of partial remissions, percentage of patients being transplanted after induction therapy and early death rate will be analysed using similar methods as with the primary analysis.

Overall survival, recurrence-free-survival and event-free survival will be analysed applying the Kaplan-Meier-method (KM). OS is calculated from the date of informed consent to the date of death, the patients still alive will be censored at the last date of follow-up. RFS is calculated from the date of informed consent to the date of recurrence or death, whichever occurs first, censoring patients who were alive without recurrence on the date of last follow-up visit. EFS is calculated from the date of CR/CRi until death or relapse, whichever occurs first. Patients are censored on the date of last follow-up visit if they are alive without relapse.

The survival curves will be displayed graphically for the overall population and by dosage schedule. In addition median survival and follow-up times (including interquartile range and 95 % CI if feasible) will be calculated.

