13.2 Laboratory safety variables

Descriptive statistics of laboratory safety variables (hematology, clinical chemistry, urine analysis, coagulation tests) will be computed, together with the changes from baseline values. The changes from baseline will be analyzed by ANOVA method if feasible.

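### Time to platelet and ANC recovery has no time-to-event analysis: the default summary covers only patients with a recovery date, overstating how complete recovery is and tending to shorten its apparent time

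*Protocol*

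**What the plan says.** Protocol 8.4.4 opens its list with "Safety evaluation will comprise the following variable and their change from baseline" and includes "Time of recovery of platelets and ANC" beside vital signs and laboratory values. The synopsis and Protocol 5.1.4 give four thresholds: platelets 50 and 100, and ANC 0.5 and 1.0 x 10^9/L.

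The protocol names no method for this item. Its general rule in 8.4.1 is: "For continuous variables, summary statistics (mean, standard deviation, median, minimum and maximum values) will be tabulated". SAP section 8 repeats that rule for safety variables and adds: "Missing values will not be imputed in the analyses". SAP 12.2 applies Kaplan-Meier to OS, RFS and EFS only.

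The SAP does not carry recovery time forward. Its safety variables (section 4) are "Adverse events (AE), blood pressure, pulse, temperature, physical examination, urine analysis, hematology, clinical chemistry, coagulation tests". Section 13.2 says "Descriptive statistics of laboratory safety variables (hematology, clinical chemistry, urine analysis, coagulation tests) will be computed, together with the changes from baseline values". The table plan (19.2) has no recovery table and the SAP schedule (19.1) has no recovery-status row.

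Collection is thorough. Note 21 to the protocol's schedule of assessments asks for blood counts often enough to fix the exact recovery date. Protocol 5.2.6 continues collection in follow-up until the thresholds are reached, and note 19 includes transplanted patients. Protocol section 10 gives the item a use: "The DMC will review safety data, recovery times and efficacy of the clinical trial".

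**The concern.** A recovery time exists only for a patient who recovers. The documents foresee patients who do not: Protocol Appendix 7 defines death in aplasia and resistant disease, and its footnote on CRi accepts that some patients may never recover fully. Under the defaults such patients contribute nothing, and the table describes a group in which everyone has recovered.

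Prolonged aplasia is a central safety question when a drug is added to 7+3 chemotherapy. The patients left out are those with the worst marrow outcome, and recovery times are among the data the DMC is asked to review.

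Transplant raises a second problem. Because recovery is followed after SCT, a date produced by the graft could be entered as recovery after Selinexor plus chemotherapy.

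**Working it through.** **No figure to reproduce.** The documents state no expected recovery time, recovery rate or precision.

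**What is specified.** I looked for four elements of a time-to-event summary: time origin, denominator, censoring rule and competing-event rule. Neither document gives any of them for recovery. What remains is the 8.4.1 default plus no imputation.

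**What the default does.** Let q be the share of patients with no recovery date and F(t) the distribution of observed recovery times. Then, whatever the shape of F:

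- share of all patients recovered by day t = (1 − q) × F(t);
- all-patient median = the 0.5/(1 − q) quantile of the observed times, which is not reached once q is 50% or more.

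F(t) alone therefore overstates the proportion recovered by a factor 1/(1 − q), and its median is too early.

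**Size on assumed inputs.** The shape, the median and q are all assumptions.

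*Illustration 1: a fixed share never recovers.* Observed times are log-normal with median m and SD of log 0.3. The all-patient median is m × exp(0.3 × z(0.5/(1 − q))), where z is the standard normal quantile. With m = 35 days:

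- q = 10%: 36.5 days (1.5 later)
- q = 20%: 38.5 days (3.5 later)
- q = 30%: 41.5 days (6.5 later)
- q = 40%: 46.8 days (11.8 later)
- q = 50%: not reached

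At q = 40%, m = 28 gives 37.4 days and m = 42 gives 56.1 days.

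*Illustration 2: a competing event can strike before recovery.* Latent recovery is log-normal (median 35 days, SD of log 0.3) and the competing time is an independent exponential tuned to give q; 1,000,000 simulated patients.

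| q | Median, patients with a date | Median, all patients | By day 42, patients with a date | By day 42, all patients |
|---|---|---|---|---|
| 10% | 34.7 | 36.2 | 74.1% | 66.7% |
| 20% | 34.3 | 37.7 | 75.1% | 60.1% |
| 30% | 33.9 | 40.1 | 76.5% | 53.6% |
| 40% | 33.5 | 44.5 | 78.0% | 46.8% |

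The median gap runs from 1.5 to 11.0 days and the day-42 gap from 7.4 to 31.2 points. With 40 patients, the standard error of the all-patient proportion is √(0.667 × 0.333/40) = 7.5 points at q = 10% and √(0.468 × 0.532/40) = 7.9 points at q = 40%. The bias is thus about 1 standard error at 10% (7.4/7.5) and about 4 at 40% (31.2/7.9).

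*Illustration 3: post-graft dates are counted.* Assume 20% never recover, a further 10%, 20% or 30% go to SCT before recovery, and their graft recovery falls on day 65 (SD 10). The reported median becomes 36.9, 39.8 or 44.6 days, against 35.0 without the transplanted patients. Reported recovery is 80%, against 70%, 60% or 50% on the regimen itself. Here the time looks slower while completeness is still overstated.

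**The case against.** The strongest reply is that neither document says recovery time will be analysed as a continuous variable or in recoverers only. The protocol lists it and leaves detail to the SAP, and the SAP omits it. A reader might infer a deliberate recoverers-only plan; the documents do not support that. What stands is that the variable is listed, collected and intended for review, and that the one default reaching it leads to that summary.

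Other stronger readings also fail:

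- *Transplanted patients drop out.* They need not: recovery status is followed after SCT (Protocol 5.2.6 and note 19). Their effect on time can go either way.
- *Patients entering a second cycle lose their recovery time.* The stated trigger is PR, and Appendix 7 defines PR with ANC above 1.0 and platelets above 100 x 10^9/L, so those patients already have recovered counts.
- *The 40 to 70% without CR/CRi implied by p1 and p0 lack recovery.* PR requires recovered counts, CRi may leave only one lineage short, and the lower thresholds (ANC 0.5, platelets 50) are compatible with CRi. This is not a non-recovery rate.
- *The DMC will see misleading tables.* Protocol section 10 does not say what form its recovery summaries take.

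It is also fair that the change-from-baseline wording is loose rather than harmful, since SAP section 8 asks for changes only where feasible. Early deaths and reasons for death are tabulated separately, so those patients are not hidden from the report. They would still be absent from the recovery summary.

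**Conclusion.** The concern holds for deaths before recovery and persistent leukemia: a summary of observed dates overstates completeness and tends to shorten the apparent time. For transplant, completeness is overstated if post-graft dates count, but the direction for time is open. The overstatement of completeness presumes that patients with a date form the denominator; none is stated.

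The size cannot be taken from the documents. On the assumed inputs (median about 35 days, SD of log 0.3), the shift in the median is about 1.5 days at 10% non-recovery, hardly worth noting, and 11 to 12 days at 40%, which would change how the marrow toxicity reads. This is a descriptive safety summary in a single-arm trial. The primary response test is unaffected. It should be corrected, but it does not threaten the main result.

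**What to change.** Add a recovery analysis to the SAP and its table plan:

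- For each of the four thresholds and each induction cycle, estimate the cumulative incidence of recovery from day 1 of that cycle in all treated patients.
- Treat as competing events, when they precede recovery: death, documented persistent leukemia or start of the next anti-leukemic therapy (where recorded), and SCT. This matches SAP addendum section 2, which already declines to credit the regimen with a response after SCT or another treatment.
- Report the proportion recovered by fixed days, for example 28 and 42, and the number of patients in each competing category.
- Remove the change-from-baseline requirement for this item in Protocol 8.4.4.

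The cost is wording and a few tables. Recovery dates and deaths are collected, and SCT dates are already needed for the censoring analysis in SAP 12.3. The weak point is the start of other therapy after end of treatment. Concomitant medication is documented only to that visit (Protocol 5.1.3) and the follow-up list in 5.2.6 does not ask for later therapy, so those dates may be incomplete and the report should say so.
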